9.7.1.1 General Considerations

Baseline core body temperature was the first rectal temperature $\geq 40.0^{\circ}\text{C}$ taken during the Screening period.

The main focus of all efficacy analyses was to describe the course of subject recovery during the study and to obtain estimates of the treatment effect. In general, all efficacy and safety variables were summarized using descriptive statistics. Continuous variables were summarized by descriptive statistics (sample size [n], mean, standard deviation [SD], 2-sided 95% confidence interval [CI] around the mean; median, minimum, and maximum).

Categorical variables and binomials (such as occurrence of events) were summarized in frequency tables which display the number and percentage of subjects reporting a particular response or outcome. All observed significance levels (“p-values”) that were reported were from 2-sided statistical tests unless otherwise specified, and were regarded as exploratory. Individual subject data were presented in listings.

All analyses, summaries, and listings were generated using SAS[®] version 9.4 or later.

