
Efficacy Parameters:
 
The main focus of all efficacy analyses was to describe the course of subject recovery during the study and to obtain estimates of the treatment effect. Any observed significance levels ("p-values") that were reported were to be regarded as exploratory, descriptive statistics.
 
The primary null hypothesis was that restoration of level of consciousness (defined as a return to GCS scores ≥ 13) in subjects with probable or definitive EHS was not different for subjects treated with Ryanodex in addition to immediate implementation of SOC (body cooling and supportive measures), compared to subjects treated with SOC only (body cooling and supportive measures) implemented immediately.
 
[REDACTED]
 
[REDACTED] the primary endpoint was the cumulative incidence of subjects who had achieved a GCS score ≥ 13 prior to or at 90 minutes post-randomization in the ITT analysis set. The number and percentage of subjects who achieved a GCS score ≥ 13 are presented by treatment arm. A two-sided 95% Wilson confidence interval (CI) for each treatment group proportion and a two-sided 95% Newcombe CI for the treatment difference were calculated. The odds ratio and its two-sided 95% CI were also calculated and reported. The cumulative incidence of subjects who achieved a GCS score
		

Name of Sponsor/Company: Eagle Pharmaceuticals, Inc.	Individual Study Table	(For National Authority Use only)
Name of Finished Product: Ryanodex® (dantrolene sodium) for injectable suspension		
Name of Active Ingredient: Dantrolene sodium		

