Secondary endpoints were analyzed for the ITT analysis set. Endpoints that consisted of actual values, changes from Baseline, or percent changes from Baseline were described by treatment group and planned time point, using basic descriptive statistics (N, mean, median, SD, two-sided 95% CI around the mean, minimum, maximum). Changes from Baseline in GCS and [REDACTED] were submitted to a repeated measures analysis employing a restricted maximum likelihood-based (REML), repeated-measure mixed model to obtain more precise estimates of treatment effect. SAS® Proc Mixed was used to perform the analysis. Each model included fixed terms for treatment group, time point, and treatment-by-time point interaction, with the Baseline value as covariate (as applicable), and subject as a random factor. An unstructured covariance matrix failed to converge when applied to pre-lock data, so a first-order autoregressive [AR (1)] covariance structure was used. An empirical ("sandwich") estimator for the variance-covariance matrix and the denominator degrees of freedom (DDFM) = BETWITHIN option for calculation of DDFM were used to take account of possible misspecification of the true covariance matrix. Predicted least square means, treatment differences between least square means, and two-sided 95% CI for the treatment differences are reported, overall and by planned time point, for all subjects in the analysis set.

Safety Parameters:

Incidence of TEAEs, serious adverse events (SAEs), related AEs, and related SAEs reported during the study was tabulated by treatment arm, overall and by maximum intensity. Deaths due to any cause during the study were tabulated by treatment arm. AEs were recorded from start of screening/randomization.

Name of Sponsor/Company: Eagle Pharmaceuticals, Inc.	Individual Study Table	(For National Authority Use only)
Name of Finished Product: Ryanodex® (dantrolene sodium) for injectable suspension		
Name of Active Ingredient: Dantrolene sodium		
Other: Demographics, subject disposition, dosing parameters, and [REDACTED] are summarized. [REDACTED]		

Name of Sponsor/Company: Eagle Pharmaceuticals, Inc.	Individual Study Table	(For National Authority Use only)
Name of Finished Product: Ryanodex® (dantrolene sodium) for injectable suspension		
Name of Active Ingredient: Dantrolene sodium		
Summary – Conclusions: Efficacy Results:		

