
 • A greater proportion of subjects treated with SOC and Ryanodex exhibited a clinically meaningful improvement in their neurological functioning (GCS ≥ 13) within 90 minutes (29.4%) and within 24 hours post-randomization (47.1%), compared to SOC only-treated subjects (11.8% and 23.5%, respectively) (ITT Analysis Set). • A greater proportion of subjects treated with SOC and Ryanodex achieved a clinically meaningful improvement (GCS score ≥ 13) in their neurological functioning as early as 45 minutes post-randomization compared to subjects treated with SOC only, and that difference in favor of the SOC and Ryanodex group remained unchanged at the end of the Treatment Phase (2 hours post-randomization) (ITT and mITT Analysis Sets). • The odds of achieving a GCS score ≥ 13 within 90 minutes post-randomization was about 3 times greater for subjects in the SOC and Ryanodex group than for subjects who received SOC only, and remained almost unchanged at or prior to 24 hours post-randomization (ITT Analysis Set). • Among fully evaluable subjects at Baseline, the odds of achieving a GCS score ≥ 13 within 90 minutes post-randomization was about 6 times greater in the SOC and Ryanodex group than for subjects who received SOC only (mITT Analysis Set). • Among fully evaluable subjects at Baseline, the mean change from Baseline in GCS score was higher in the SOC and Ryanodex group (3.1; $p=0.017$) compared with the SOC only group (1.1; $p=0.179$); the mean percent change from Baseline in GCS score was also higher in the SOC and Ryanodex group (55.6%; $p=0.073$) compared with the SOC only group (20.2%; $p=0.212$). In both cases, the within-group p-value clearly favors the SOC and Ryanodex group, compared with the SOC only group (mITT Analysis Set). • The proportion of subjects who achieved complete normalization in their level of consciousness (GCS score = 15) was greatest at 24 hours post-randomization and was greatest in the SOC and Ryanodex group (41.2%) than in the SOC only group (23.5%) (ITT Analysis Set). • Duration of SOC was substantially shorter in the SOC and Ryanodex group compared to the SOC only group (ITT Analysis Set). • The time to reach first rectal temperature $\leq 38^{\circ}\text{C}$ was similar in both treatment groups (ITT Analysis Set). • The median time to reach first rectal temperature $\leq 38^{\circ}\text{C}$ was shorter in the SOC and Ryanodex group (90.0 minutes) than in the SOC only group (103.0 minutes). In addition, the time at which at least 75% of the subjects had first rectal temperature $\leq 38^{\circ}\text{C}$ was also shorter in the SOC and Ryanodex group (125.0 minutes) than in the SOC only group (195.0 minutes) (mITT Analysis Set). • Overall mean cooling rates were similar in both treatment groups (ITT and mITT Analysis Sets). 
Subjects treated with Ryanodex in addition to SOC, exhibited greater clinically meaningful improvement in their neurological functioning compared to SOC only-treated subjects. The observed incremental improvement in neurologic functioning constitutes a clinically relevant benefit, known to be associated
		

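### The synopsis treats two within-arm p-values for GCS change in the mITT set as evidence that Ryanodex is better; they do not compare the arms, and no between-arm estimate is given

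*Combined protocol and SAP*

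**What the plan says.** The Synopsis of the Combined protocol and SAP (section 2.0, Efficacy Results) has a bullet on subjects fully evaluable at Baseline (mITT). It reports two measures, each with one p-value per arm, and calls those p-values within-group:

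- mean change in GCS: 3.1 (p=0.017) with SOC and Ryanodex, 1.1 (p=0.179) with SOC only;
- mean percent change in GCS: 55.6% (p=0.073) and 20.2% (p=0.212).

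It concludes: "In both cases, the within-group p-value clearly favors the SOC and Ryanodex group, compared with the SOC only group".

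The methods part of the same Synopsis sets a different standard. The main focus of the efficacy analyses was "to describe the course of subject recovery during the study and to obtain estimates of the treatment effect", and any p-values "that were reported were to be regarded as exploratory, descriptive statistics". The SAP, section 9.7.1.1, says of all reported p-values that they were two-sided unless otherwise specified "and were regarded as exploratory". For change in GCS the Synopsis describes a repeated-measures mixed model and states: "Predicted least square means, treatment differences between least square means, and two-sided 95% CI for the treatment differences are reported". These results are given both across all time points and separately at each one.

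On the analysis set, the Synopsis says: "Secondary endpoints were analyzed for the ITT analysis set". The SAP, section 9.7.1.9.3, lists change and percent change in GCS for ITT and for a second set whose name is redacted.

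**The concern.** A within-arm p-value asks whether that arm moved from its own baseline. In treated heat stroke some recovery is expected in both arms, so the answer says little about the added drug. It also depends on that arm's spread and size as well as its mean. One arm can fall below 0.05 and the other above it while the difference between them is poorly determined. Randomisation supports the between-arm contrast, and that is the quantity the bullet leaves out.

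The wording makes this worse. It draws a comparative conclusion from values that the documents class as exploratory, and it does so with the word clearly. It claims this for both measures, although neither percent-change value is below 0.05. A reader of the Synopsis alone could take the sentence as statistical evidence of a treatment difference in mean GCS, which the printed figures do not supply.

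**Working it through.** **What can be reproduced.** The within-arm p-values cannot be re-derived: the visible text gives no SD, no standard error, no mITT arm size and no name for the test. The step below works backwards from the printed means and p-values to see what between-arm contrast they imply.

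**Inputs**
- Means and p-values: the mITT bullet, as listed above.
- Differences: 3.1 − 1.1 = 2.0 GCS points; 55.6 − 20.2 = 35.4 percentage points.
- Arm size, ceiling: 17. The Synopsis gives 34 subjects analysed, and its ITT responder rates at 90 minutes fit 5/17 = 29.4% and 2/17 = 11.8%. The mITT set is a subset of ITT (SAP, section 9.7.1).
- Arm size, floor: 6, which is an assumption.
- Further assumptions: each p-value is a two-sided one-sample t-test of the mean against zero, and the arms are independent.

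**Formulas** (n and m are the arm sizes; A is Ryanodex, B is SOC only)
- SE_A = mean_A / t(1 − p_A/2; n − 1), and SE_B likewise with m − 1
- SE_diff = √(SE_A² + SE_B²), with Welch degrees of freedom

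**Worked case, 10 per arm**
- Change in GCS: SE_A = 3.1/2.921 = 1.061; SE_B = 1.1/1.457 = 0.755; SE_diff = 1.302. Then t = 2.0/1.302 = 1.536 on 16.25 df, p = 0.144, 95% CI −0.8 to 4.8.
- Percent change: SE_A = 55.6/2.029 = 27.40; SE_B = 20.2/1.3435 = 15.04; SE_diff = 31.25. Then t = 35.4/31.25 = 1.133 on 13.97 df, p = 0.276, 95% CI −32 to 102.

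**Over the range**

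| Subjects per arm | Change in GCS, difference 2.0: p (95% CI) | Percent change, difference 35.4: p (95% CI) |
|---|---|---|
| 6 | 0.108 (−0.5 to 4.5) | 0.247 (−30 to 101) |
| 10 | 0.144 (−0.8 to 4.8) | 0.276 (−32 to 102) |
| 17 | 0.165 (−0.9 to 4.9) | 0.292 (−32 to 103) |
| Normal limit | 0.193 (−1.0 to 5.0) | 0.312 (−33 to 104) |

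Unequal arms between 6 and 17 stay inside these p-value ranges.

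**Sensitivity to the floor.** With 4 per arm, p is 0.068 (CI −0.2 to 4.2) for change and 0.202 for percent change. With 3 per arm, the interval for change just excludes zero (p = 0.046, CI 0.06 to 3.94). That would require 14 of 17 subjects in each arm to fall outside the mITT set.

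**The case against.** The best defence has four parts.

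1. The plan itself is sound: the mixed model gives the right contrast, so this is a fault of reporting and not of analysis. That is correct, and the model is not criticised here.
2. The documents label p-values exploratory, and the bullet openly says within-group, so a careful reader can see what was tested. This softens the fault but does not remove it. An exploratory between-arm estimate would be acceptable; a within-arm p-value is not one.
3. The consequence is limited. The overall conclusion speaks of clinically meaningful improvement, which the Synopsis ties to GCS ≥13, and those results do not use this bullet. This stands, and it limits the weight of the point.
4. The back-calculation rests on an unseen test, unseen arm sizes and a chosen floor, and the mixed model could give other values. This also stands. The figures illustrate the problem but are not evidence for it.

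It is also fair to say that a between-arm interval is shown to be missing only from this bullet. The Synopsis says such differences are reported, and whether the mITT contrast already exists cannot be settled from the visible text.

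**Conclusion.** The concern holds. The sentence draws a comparison between arms from tests that make none, and for percent change it has no support even from the usual 0.05 threshold. This conclusion needs no assumption, because the document itself describes the p-values as within-group.

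The size is indicative only. With t-type tests, independent arms and 6 to 17 subjects per arm, the implied between-arm intervals include zero for both measures; much smaller arms or another test could change that. The scope is one exploratory secondary result in the mITT set. It should be fixed, but it does not touch the responder results.

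**What to change.** - Delete the sentence, and do not use within-arm p-values as evidence of a treatment effect.
- For change in GCS, quote the LS-mean difference (Ryanodex minus SOC only) with its 95% CI from the mixed model described in the Synopsis. Give it for mITT and for ITT, with the number per arm. State the time point, or say that it is the overall estimate: the bullet names none, and the model yields both kinds.
- Say whether 3.1 and 1.1 are observed or model-based means. If they are observed, they need not differ by exactly the LS-mean difference.
- For percent change, either give a between-arm difference with its 95% CI or leave it descriptive, without p-values.

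Possible wording: *Mean change in GCS at [time point] was 3.1 (SOC and Ryanodex, n=__) and 1.1 (SOC only, n=__); LS-mean difference __ (95% CI __ to __), exploratory.*

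The cost is small: a less favourable sentence and, if the mITT contrast has not been produced, one short additional run of the existing model.

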2.0 SYNOPSIS

Name of Sponsor/Company: Eagle Pharmaceuticals, Inc.	Individual Study Table	(For National Authority Use only)
Name of Finished Product: Ryanodex® (dantrolene sodium) for injectable suspension		
Name of Active Ingredient: Dantrolene sodium		
Title of Study: Phase 2, Single-Site, Open-Label, Randomized, 2-Arm Parallel Study to Assess the Efficacy and Safety of Ryanodex® (EGL-4104) as Adjuvant Treatment in Subjects With Exertional Heat Stroke (EHS)		
Investigators: [REDACTED]		
Study Centers: The study was conducted at a single site with 3 additional satellite site locations in the region of Mekkah, Saudi Arabia, during the 2015 Hajj pilgrimage.		
Publication (Reference): None		
Study Period: 22 September 2015 (First Subject Enrolled) - 27 September 2015 (Last Subject Completed Treatment)	Phase of Development: 2	
Objectives: Primary : To evaluate the efficacy of Ryanodex for the treatment of EHS, administered as adjunctive treatment to current standard of care (SOC). Secondary : To evaluate the safety and tolerability of Ryanodex for the treatment of EHS by comparing the treatment groups for the incidence of treatment-emergent adverse events (TEAEs), physical and neurological examination findings, clinical laboratory test results, and vital signs.		
Methodology: [REDACTED]		

Name of Sponsor/Company:	Individual Study Table	(For National Authority Use only)
Eagle Pharmaceuticals, Inc.		
Name of Finished Product:		
Ryanodex® (dantrolene sodium) for injectable suspension		
Name of Active Ingredient:		
Dantrolene sodium		

Treatment Groups:

Upon admission to the emergency medical facility and following assessment of study inclusion and exclusion criteria, eligible subjects with probable or definitive EHS were randomized in a 1:1 ratio to one of the following treatment groups:

- Group A: Ryanodex, in addition to immediate implementation of SOC (body cooling and supportive measures)
- Group B: SOC only (body cooling and supportive measures) implemented immediately

Subjects randomized to Group A received an initial dose of Ryanodex (study drug) of 2 mg/kg administered as an IV bolus, in addition to SOC. If the subject did not show adequate clinical response between 30 and 90 minutes after the initial dose, a single repeat dosing of 2 mg/kg of study drug could be administered between 30 and 90 minutes following the initial dose.

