Subjects who had received up to two 2-mg/kg (up to 4 mg/kg) IV doses of Ryanodex (Group A) during the Treatment Phase of the study could receive additional treatment with Ryanodex at a dose of 1 mg/kg as an IV bolus starting at 90 minutes following the initial dose and continuing every 6 hours for up to 24 hours under the following conditions:

1. If the subject had not achieved an adequate response (defined as rectal temperature $\leq 38.0^{\circ}\text{C}$ and Glasgow Coma Scale (GCS) score ≥ 13); or,
2. If the subject had achieved an adequate response (defined as rectal temperature $\leq 38.0^{\circ}\text{C}$ and GCS ≥ 13) but the symptoms began to reappear

Clinical assessments and symptoms leading to additional doses of study drug were to be clearly recorded. The total administered dose of Ryanodex in a [REDACTED] period was not to exceed [REDACTED]

Stopping the study drug:

If [REDACTED]

The study protocol included three phases (Screening/Randomization, Treatment Phase, and Follow-up

Name of Sponsor/Company: Eagle Pharmaceuticals, Inc.	Individual Study Table	(For National Authority Use only)
Name of Finished Product: Ryanodex® (dantrolene sodium) for injectable suspension		
Name of Active Ingredient: Dantrolene sodium Phase), plus a follow-up contact by telephone at approximately [REDACTED] days after the subject's discharge from the study.		
Number of Subjects (Planned and Analyzed): A total of 100 subjects (50 per arm) were initially planned to be randomized in the study. Due to unforeseen tragic events impacting the location of the study and enrollment plans, 40 subjects were screened to participate, and 34 subjects were randomized (6 subjects were screen failures). A total of 34 subjects were analyzed for efficacy and safety.		
Diagnosis and Main Criteria for Inclusion: Male or non-pregnant female subjects were entered into this study if they were diagnosed with probable or definitive EHS as evidenced by all of the following: 
 • A core body temperature obtained rectally of $\geq 40.0^{\circ}\text{C}$ (104.0°F) • In the judgment of the Investigator, the subject was likely 18 years of age or older, and not older than 45 years of age • Recent history or suspected recent history (prior 24 hours) of performing intense physical activity (exertional activity) • The subject had impaired consciousness level as evidenced by a GCS score < 13 • The subject had tachycardia (heart rate ≥ 100 beats per minute [bpm]). 		

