
Name of Sponsor/Company: Eagle Pharmaceuticals, Inc.	Individual Study Table	(For National Authority Use only)
Name of Finished Product: Ryanodex® (dantrolene sodium) for injectable suspension		
Name of Active Ingredient: Dantrolene sodium		
with lower risk of EHS-related complications, and decreased long-term morbidity and mortality.		

Safety Results:
 
 • Ryanodex was safe and well-tolerated by subjects in the SOC and Ryanodex group. • No new and/or unexpected safety signals were detected. • The overall incidence of TEAEs was similar in both groups. • No treatment-related TEAEs were reported. • No subjects withdrew due to TEAEs. • There were no clinically meaningful differences in laboratory abnormalities between the two treatment groups. • There were no clinically meaningful differences in vital signs, ECGs, ETCO₂, or oxygen saturation between the two treatment groups. • The safety profile of Ryanodex in this study population was consistent with the known and well-characterized safety profile in the currently approved indications. 		

Conclusion:
 
Overall, Ryanodex administered to EHS subjects was safe and well tolerated. The safety profile of Ryanodex in this severely ill population was consistent with its known and well-characterized safety profile in the currently approved indications.
 
Subjects treated with Ryanodex, in addition to SOC, exhibited greater clinically meaningful improvement in their neurological functioning compared to SOC only-treated subjects. The observed incremental improvement in neurologic functioning constitutes a clinically relevant benefit, known to be associated with lower risk of EHS-related complications, and decreased long-term morbidity and mortality.
 
The results of the study provide clinical evidence of the therapeutic benefit that Ryanodex may deliver to patients with EHS.

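### The synopsis concludes that Ryanodex was safe and well tolerated, with TEAE incidence similar to SOC, but gives no count, denominator or interval, and only about 17 subjects were exposed

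*Combined protocol and SAP*

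**What the plan says.** The secondary objective (Combined document, Section 2.0 Synopsis, Objectives) is to evaluate safety and tolerability by comparing the treatment groups on TEAEs, examination findings, laboratory tests and vital signs.

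The synopsis then reports, under Safety Results:

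- "Ryanodex was safe and well-tolerated by subjects in the SOC and Ryanodex group"
- "No treatment-related TEAEs were reported"
- "The overall incidence of TEAEs was similar in both groups"

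It also reports no withdrawals due to TEAEs, no clinically meaningful arm differences in laboratory values, vital signs, ECG, ETCO₂ or oxygen saturation, and consistency with the profile in the approved indications. The Conclusion repeats the safety and tolerability statement without limiting it to the treated group and extends the known-profile statement to this severely ill population.

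On size, the synopsis planned 100 subjects, and subjects were "randomized in a 1:1 ratio to one of the following treatment groups". In the event, "A total of 34 subjects were analyzed for efficacy and safety". The Safety set is classified by treatment actually received and the ITT set by planned treatment (Synopsis, Analysis sets).

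On method, the primary endpoint gets a Wilson interval for each arm and a Newcombe interval for the difference (SAP 9.7.1.9.1; Synopsis, Efficacy Parameters). For adverse events the visible text specifies numbers of events and incidence rates by arm and names no interval (SAP 9.7.1.1 and 9.7.1.10.1; Synopsis, Safety Parameters).

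**The concern.** The safety analysis was set up as a descriptive tabulation, and the report draws a categorical verdict from it. Absence of related events in a very small group says little about the underlying rate. Not seeing a difference between two very small groups says little about similarity. Without a denominator or an interval, a reader of the synopsis cannot see how weak the evidence is.

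The study was also open-label, and the visible text describes no blinded assessment of relatedness. The count of related events therefore depends on that assessment as well as on sample size.

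At stake is what the trial may claim on its stated secondary objective, in a patient group outside the approved indications to which the report appeals.

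**Working it through.** **1. Arm size.** The documents do not state it. Inputs are the 34 subjects and the ITT percentages in the synopsis Efficacy Results: "within 90 minutes (29.4%) and within 24 hours post-randomization (47.1%), compared to SOC only-treated subjects (11.8% and 23.5%, respectively" and, for GCS 15 at 24 hours, "greatest in the SOC and Ryanodex group (41.2%) than in the SOC only group (23.5".

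Of all splits summing to 34, only 17/17 reproduces all six percentages to one decimal:

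- SOC and Ryanodex: 5/17 = 29.4%, 8/17 = 47.1%, 7/17 = 41.2%
- SOC only: 2/17 = 11.8%, 4/17 = 23.5%, 4/17 = 23.5%

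Check against the report's own odds ratio, described as about 3 at 90 minutes and almost unchanged at 24 hours:

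- 90 minutes: (5/12)/(2/15) = 3.13
- 24 hours: (8/9)/(4/13) = 2.89

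Both agree. *Assumption:* the 17 in planned Group A all received drug and nobody crossed over, so that exposed n = 17.

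**2. Upper 95% limit for 0 related TEAEs in n = 17.**

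- Exact two-sided (Clopper-Pearson): 1 − 0.025^(1/17) = 19.5%
- Wilson: z²/(n + z²) = 3.84/(17 + 3.84) = 18.4%
- Exact one-sided: 1 − 0.05^(1/17) = 16.2%

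If the assumption is off by one, the exact two-sided limit is 20.6% for n = 16 and 18.5% for n = 18.

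**3. Chance of seeing no event in 17, (1 − p)^17, for a true rate p.**

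- p = 5%: 0.95^17 = 41.8%
- p = 10%: 0.90^17 = 16.7%
- p = 15%: 0.85^17 = 6.3%
- p = 20%: 0.80^17 = 2.3%

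**4. What similar incidence could mean.** The supplied text gives no TEAE counts, so this step is an illustration with assumed counts. With equal observed proportions p in both arms and Wilson limits l and u, the Newcombe half-width is √[(p − l)² + (u − p)²]:

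- 0/17 each: l = 0, u = 0.184, half-width 18 points
- 2/17 each: 24 points
- 4/17 each: 28 points
- 8/17 each: 30 points
- 12/17 each: 29 points
- 15/17 each: 24 points

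Even identical observed rates would leave differences of about 18 to 30 points in either direction compatible with the data.

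**The case against.** The best defence is that safety was always descriptive. SAP 9.7.1.1 says that safety variables were summarized with descriptive statistics, no safety hypothesis or non-inferiority margin is visible, and TEAEs, SAEs, related events and deaths were tabulated by arm as planned. The Safety Results sentence is limited to subjects in the treated group, and the other statements are past-tense observations. This stands to the extent that the report did not depart from its plan, and a reader should not infer that it did. It does not rescue the wording. A descriptive tabulation cannot carry an unqualified verdict, and the Conclusion drops the limitation to the treated group.

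Four stronger readings are tempting, and the documents do not support them:

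- *That 17 exposed is a reported fact.* It is inferred from planned-arm percentages, whereas the Safety set follows actual treatment.
- *That the report contains no safety interval anywhere.* Much of SAP 9.7.1.10.2 to 9.7.1.10.4 is redacted, and the report body and tables were not supplied. The absence can be claimed only for the visible synopsis and adverse-event methods.
- *That the safety conclusion rests on zero related events alone.* It also cites overall TEAEs, withdrawals, laboratory and vital-sign findings, and the known profile. The 0/17 bound does not address those items, although the evidence from this trial is limited by the same sample size.
- *That the ±18 and ±30 point widths are this trial's results.* They follow from assumed counts.

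**Conclusion.** The point holds as a reporting correction. The visible synopsis states safety and similarity without the count, denominator or interval that would let them be weighed, and the sample cannot establish either. With about 17 exposed, zero related TEAEs is compatible with a true rate of up to 16% to 20%, depending on the method. An event with a true rate of 10% would be missed entirely about one time in six. For similarity, the size cannot be stated without the TEAE counts, but at 17 per arm no equal observed rate would exclude a difference of under about 18 points.

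This is a statement about precision. A reader might infer that Ryanodex was unsafe, or that the related-event rate is near 20%. The documents support neither. A true rate of 20% would give zero events in 17 only 2.3% of the time, so that figure marks the edge of what the data allow.

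The conclusion rests on exposed n being at or near 17. A change of one subject either way moves the exact limit by about one point and does not alter it.

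**What to change.** In both Safety Results and Conclusion, replace the unqualified safety and similarity statements with the observed result, for example: *no treatment-related TEAE was reported in n exposed subjects (95% CI, method named); the sample is too small to establish safety or similarity to SOC.* Take n from the Safety set by actual treatment, not from the 17 inferred here. Name the interval method, since the choice moves the limit by up to three points. Wilson would match the primary endpoint.

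Add the Newcombe 95% interval, already used for the primary endpoint, to the arm differences in overall TEAEs, SAEs and deaths, unless the report body already gives it. If it does, carry it into the synopsis.

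The cost is small. No new data are needed, because these events are already tabulated by arm. It takes a little more tabulation and some rewording, and the safety conclusion becomes less favourable.
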